5.3 Dose Escalation (Phase 1b PLX2853 + Carboplatin Only)

In Phase 1b (PLX2853 + carboplatin combination) dose escalation, cohorts will be enrolled using a standard "3+3" design. The starting dose level of PLX2853 will be 40 mg/day plus a target AUC of 5 mg•min/mL dose of carboplatin (Cohort 1). In the absence of a DLT in the first cycle of treatment and in conjunction with review of the PK and available PDx data from each cohort by the Study Committee, dose escalation is planned to occur in the following manner:

• DLTs will be assessed in the first treatment cycle (up to carboplatin dosing on Cycle 2 Day 1).

- The starting dose of PLX2853 will be 40 mg/day (Cohort 1), which is 50% below the PLX2853 monotherapy RP2D of 80 mg/day.
- Carboplatin will be administered using a target AUC of 5 mg•min/mL on Day 1 of each 28-day treatment cycle per label. Carboplatin must be given within 7 days of Cycle 2 Day 1 (delays due to reasons other than toxicity will not be assessed as a DLT).
- If Dose Level 1 is not tolerated, Dose Level -1 (20 mg/day) will be investigated. If that dose level is intolerable, Dose Level -2 (PLX2853 20 mg/day + carboplatin AUC 4 mg•min/mL) will be studied. If that dose level is intolerable, the study will be halted.
- In the absence of a DLT, a second cohort with a PLX2853 dose of 80 mg/day will be investigated (Cohort 2).

5.3.1 Dose Escalation Rules

Dose escalation will occur in accordance with the following rules:

- A minimum of 3 to 4 subjects will be initially enrolled in Cohort 1.
- If a DLT is observed in 1 subject in a given cohort, up to 6 subjects will be treated at that dose.
- If DLTs are observed in 2 or more of 6 subjects (or ≥33% of the cohort) at a dose level, the
 dose at which this occurs will be considered intolerable and the MTD will have been
 exceeded.
- The highest dose level at which 0 of 3 subjects or 0 or 1 of 6 subjects experience a DLT will be declared the RP2D. If 3 to 4 subjects were initially evaluated at that dose level, an additional 2 to 3 subjects may be enrolled to evaluate for DLTs at that dose level for confirmation. Up to 6 additional subjects with a known ARID1A mutation (unless otherwise approved by the Medical Monitor) may be treated at the RP2D at the discretion of the Sponsor for dose confirmation purposes.
- In order to be DLT evaluable a subject must not have missed more than 25% of study drug for reasons other than AE and must not have missed receiving carboplatin within 7 days of Cycle 2 Day 1 (if applicable) for reason other than AE. If a subject misses more than 25% of the doses for Cycle 1 (e.g., >7 doses of PLX2853 in 28 days) during the DLT window for reasons other than an AE, additional subject(s) may be enrolled to provide adequate data for dose escalation decision making. Subjects who do not complete Cycle 1 for reasons other than drug toxicity may be replaced. Subjects must receive their Cycle 2 Day 1 carboplatin dose to be considered evaluable unless the reason for missing carboplatin is due to an AE.

- Once all ongoing subjects in a dose cohort have been treated for at least 2 cycles and the safety and tolerability of that dose level has been established, intra-subject dose escalation to that dose level may be permitted for subjects enrolled at lower dose levels who have not experienced an unresolved Grade 3 or higher treatment-related toxicity and have completed 2 cycles. Any intra-subject dose escalation requires a discussion and agreement with the Medical Monitor.
- After dosing has been completed in each cohort, safety, PK, and PDx data (if available) will be reviewed, and dose escalation decisions will be made by the Study Committee. Dose escalation decisions will also take into consideration safety information beyond the DLT period from earlier cohorts.
- If no DLT is observed, the recommended dose for further evaluation may be established based on toxicity, PK, convenience of dosing, and PDx (if available) in subjects treated at that dose. Dose escalation will only be permitted if adequate safety and tolerability have been demonstrated at the previous lower dose for 28 days.
- PLX2853 and carboplatin may not be dose escalated in the same cycle.

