The study will employ a standard 3 + 3 design in order to determine the MTD/RP2D taking into consideration safety, PK, and PDx data (if applicable).

Data will be tabulated and evaluated by descriptive statistics. Statistical analyses for the primary objectives will be descriptive only, with no hypothesis testing. Summary tables will present results for each dose cohort. Descriptive statistics will be presented for continuous variables, and frequencies and percentages will be presented for categorical and ordinal variables.

Response to treatment will be evaluated by investigator-determined response using RECIST v1.1 criteria.

Phase 2a (PLX2853 Monotherapy) and Phase 2a (PLX2853 + carboplatin combination):

The primary objectives of the Phase 2a cohorts of the study are to determine the antitumor activity (ORR) of PLX2853 monotherapy or PLX2853 + carboplatin combination. Response to treatment will be evaluated using investigator-determined RECIST v1.1 criteria, with a minimum interval for confirmation of CR and PR of 4 weeks. Each Phase 2a cohort will enroll up to 26 evaluable subjects using a Simon's 2-stage design in which initially 12 evaluable subjects are enrolled. In the monotherapy cohort, the safety lead in of 6 subjects dosed at the level selected for Phase 2a will be included in the group of 12 evaluable subjects for stage 1. If \geq 33% DLTs are seen during the initial safety lead in, the Safety Committee will convene to consider a dose reduction. If a dose reduction is deemed appropriate, the subjects in the initial safety lead in will need to be replaced and a repeat 6 subject safety lead in will need to be conducted at this lower dose. If 2 or more responses are observed in 12 evaluable subjects, another 14 evaluable subjects will be enrolled for a total of 26 subjects to that cohort. If 6 or more responses are observed, the study has 80% power with alpha of 0.05 to reject the ORR of 10% in favor of the ORR of 30%. Recruitment will stop within a cohort if no more than 1 response is observed after the initial 12 evaluable subjects have been accrued. ORR will be summarized per cohort along with their 95% confidence intervals (CIs). A 2-sided 95% CI will be calculated for the true response rate based on the Clopper Pearson method.

PLX2853 Protocol PLX124-03/Amendment 2

SYNOPSIS TABLE 1: PHASE 2A PLX2853 MONOTHERAPY SCHEDULE OF EVENTS

ASSESSMENTS ▼	PROCEDURE ▼	SCR1	C1		C2	C3+ ²					

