As of 22 March 2021, the most common adverse events (AEs) associated with PLX2853 reported in >10% of subjects are nausea, fatigue, diarrhea, decreased appetite, dysgeusia, anemia, hyperbilirubinemia, and vomiting. Less common side effects associated with PLX2853 recorded

in 5% to 10% of subjects are dehydration, dizziness, dry mouth, gastroesophageal reflux disease, decreased platelet count, hyponatremia, increased aspartate aminotransferase, and white blood cell count decreased.

As of 22 March 2021, 1 DLT has been reported in Study PLX124-03: Grade 3 hyponatremia at a dose of 80 mg/day PLX2853 + carboplatin AUC 5 (mg•min/mL). Four DLTs have been reported in Study PLX124-01: 2 events of Grade 4 thrombocytopenia at 120 mg/day PLX2853; 1 dose reduction in Cycle 1 for \geq Grade 2 AE (Grade 3 fatigue, Grade 2 cheilitis, Grade 2 nausea) at 40 mg BID (80 mg total/day); and 1 dose reduction in Cycle 1 for \geq Grade 2 AE (Grade 3 thrombocytopenia) at 60 mg BID (120 mg total/day). Two DLTs have been reported in Study PLX124-02: Grade 3 hyperbilirubinemia at a dose of 180 mg/day; Grade 4 hyperbilirubinemia at a dose of 140 mg/day.

Refer to the Reference Safety Information section of the Investigator's Brochure for additional safety information.

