After dosing has been completed in each cohort, safety, PK, and PDx data (if available) will be reviewed, and dose escalation decisions will be made by the Study Committee. Dose escalation decisions will also take into consideration safety information beyond the DLT period from earlier cohorts. If no DLT is observed, the recommended dose for further evaluation may be established based on toxicity, PK, convenience of dosing, and PDx (if available) in subjects treated at that dose. Dose escalation will only be permitted if adequate safety and tolerability have been demonstrated at the previous lower dose for 28 days. PLX2853 and carboplatin may not be dose escalated in the same cycle.

PLX2853 PK data will be analyzed in each dosing cohort for C_{max}, AUC, and accumulation ratio at steady state and compared with prior dose levels. The number of subjects at a given dose level may be increased as a result of the review of safety, observed or anticipated disease activity, and PK data. Additional dosing schedules may be studied, such as alternate day dosing (e.g., every other day) depending on emerging safety and PK data.

In Phase 2a (dose expansion), efficacy as well as additional safety, PK, and PDx data of PLX2853 in combination with carboplatin at the RP2D dose established in Phase 1b by the Study Committee will be obtained using a Simon's 2-stage design.

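### The Phase 1b intolerability trigger of ≥33% of the cohort is met by 1 DLT in 3 subjects, a result the preceding rule sends to expansion to 6

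*Combined protocol and SAP*

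**What the plan says.** Phase 1b sets the dose of PLX2853 with carboplatin, and the MTD/RP2D is its primary endpoint (Section 3.4.1). The synopsis, under Statistical Considerations, states: "The study will employ a standard 3 + 3 design in order to determine the MTD/RP2D". Section 5.3.1 then gives the rules:

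- Starting size: "A minimum of 3 to 4 subjects will be initially enrolled in Cohort 1".
- Expansion: "If a DLT is observed in 1 subject in a given cohort, up to 6 subjects will be treated" at that dose.
- Intolerability: "If DLTs are observed in 2 or more of 6 subjects (or ≥33% of the cohort) at a dose level", the dose is intolerable and the MTD has been exceeded.
- Selection: the highest level at which "0 of 3 subjects or 0 or 1 of 6 subjects experience a DLT will be declared the RP2D".

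The same rules stand in Section 3.1.2 and in the Phase 1b part of the synopsis. Section 3.1.2 also allows larger cohorts: "The number of subjects at a given dose level may be increased as a result of the review of safety", disease activity and PK data.

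**The concern.** The percentage in the intolerability bullet is joined by 'or' and has no floor. One DLT among 3 evaluable subjects is 33.3%, so two adjacent mandatory rules apply to the same result with opposite consequences: treat up to 6, or reject the dose. Three is the basic cohort size of the design, and 1 of 3 is the result that a 3+3 expansion step exists to resolve.

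The Phase 2a combination dose follows from this decision. Literal rejection of Dose Level 2 would leave 40 mg/day. Literal rejection of Dose Level 1 would send the study to 20 mg/day, although Section 1.5.4 reports that a consistent pharmacodynamic effect was first seen at 40 mg/day. At Dose Level -2 it would halt the study.

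The case is realistic. Section 1.7 reports that "1 DLT has been reported in Study PLX124-03: Grade 3 hyponatremia at a dose of 80 mg/day PLX2853 + carboplatin AUC 5", which is the top planned level. The size of that cohort is not given, so it is not known whether this was 1 of 3.

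**Working it through.** **Inputs.** Starting size 3 or 4, expansion to 6 after one DLT, and the trigger of 2 of 6 or ≥33% all come from Section 5.3.1. The documents give no true DLT rate, so p = 10%, 20% and 30% are assumed.

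**Step 1: the plan's own pair of figures.** 2/6 = 33.3%, which is ≥33%. The count and the percentage agree at n = 6.

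**Step 2: other cohort sizes.** One DLT gives 1/3 = 33.3% (met), 1/4 = 25%, 1/5 = 20% and 1/6 = 16.7% (not met). The smallest number of subjects with a DLT that meets each rule is:

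| Cohort size n | 3 | 4 | 5 | 6 | 7–9 | 10–12 |
|---|---|---|---|---|---|---|
| ≥33% as written | 1 | 2 | 2 | 2 | 3 | 4 |
| ≥2 subjects and ≥33% | 2 | 2 | 2 | 2 | 3 | 4 |

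The rows differ only at n = 3. Elsewhere the percentage does useful work: it stops a cohort early at 2 of 3, 2 of 4 or 2 of 5, and it covers levels with more than 6 subjects.

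**Step 3: probability that one dose level is declared intolerable, starting with 3.** Let a = P(0 of 3) = (1−p)³ and b = P(1 of 3) = 3p(1−p)².

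- Expansion reading: tolerated after 0 of 3, or after 1 of 3 followed by 0 of 3, so P(intolerable) = 1 − (a + b·a).
- Literal reading: tolerated only after 0 of 3, so P(intolerable) = 1 − a.
- Gap = b·a.

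| p | a | b | Expansion | Literal | Gap (points) |
|---|---|---|---|---|---|
| 10% | 0.729 | 0.243 | 9.4% | 27.1% | 17.7 |
| 20% | 0.512 | 0.384 | 29.1% | 48.8% | 19.7 |
| 30% | 0.343 | 0.441 | 50.6% | 65.7% | 15.1 |

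For p = 20%: 1 − (0.512 + 0.384 × 0.512) = 1 − 0.709 = 0.291, against 1 − 0.512 = 0.488.

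Column b is how often a cohort of 3 shows exactly one DLT (24%, 38%, 44%). Column a is also the share of those cohorts that would finish at an acceptable 1 of 6 if expanded (73%, 51%, 34%).

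**Step 4: starting with 4.** One of 4 does not reach 33%, so both readings expand by 2 subjects. P(intolerable) = 1 − [(1−p)⁴ + 4p(1−p)³·(1−p)²] = 10.8%, 32.8% and 55.8%. The gap is zero.

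**The case against.** The best defence is that the text resolves itself. The expansion bullet deals specifically with exactly one affected subject. The next bullet moves to two or more, and its parenthesis is most naturally the proportional form of that rule for other cohort sizes. The monotherapy lead-in uses 33% in this way, on 6 subjects, where it means 2 of 6. The cohort could also mean the enlarged cohort, since escalation decisions follow completion of dosing in a cohort. The 3+3 label and the acceptance of 1 of 6 point the same way. Further, the error can only be cautious, a committee that includes the Medical Monitor and the Principal Investigators decides (Section 7.1.2), Phase 1b involves no hypothesis testing, and the probability gap assumes that the committee follows the less plausible reading every time.

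Most of this stands as evidence of intent, and it limits the severity. The figures at n = 3 are an upper bound, and the bullet on the RP2D foresees 3 to 4 initial subjects at whichever level is chosen, so cohorts of 4, with no gap, are not confined to Cohort 1. The reported DLT at 80 mg/day does not show that the literal reading was ever used.

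It does not remove the defect. The word 'or' makes the percentage a separate trigger, nothing defines the cohort as the enlarged one, and no sentence sets precedence. A literal reader also has some support: Section 6.1 lets escalation be halted when cumulative toxicities require dose reductions in 1 of 3 subjects, though that rule is discretionary and concerns later cycles. A committee should not have to choose between two mandatory rules after seeing the data.

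**Conclusion.** The concern holds. The ≥33% trigger is wrong as written for a cohort of 3 and correct at every other size checked (4 to 12). Read literally, it raises the chance of rejecting one dose level by 18, 20 and 15 percentage points at true DLT rates of 10%, 20% and 30%. These figures assume 3 starting subjects, independent outcomes with a common DLT rate, and a committee that puts the percentage ahead of the expansion bullet. With 4 starting subjects, or if the committee follows the expansion bullet, there is no effect.

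Severity is moderate. The risk is of discarding a usable dose, not of overdosing, and the intended rule can be inferred. It should still be corrected, because this threshold decides the Phase 1b primary endpoint and the dose carried into Phase 2a.

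**What to change.** In Section 5.3.1, Section 3.1.2 and the synopsis, replace the condition in the intolerability sentence with: *if at least 2 subjects, and ≥33% of the subjects in the cohort, experience a DLT at a dose level*. Leave the stated consequence unchanged.

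This sends 1 of 3 to expansion only. It keeps the early stop at 2 of 3, 2 of 4 and 2 of 5, keeps 2 of 6, and leaves larger cohorts as they are (3 of 7 to 9, 4 of 10 to 12). Simpler edits fail: >33% still catches 1 of 3, and >1/3 would let 2 of 6 pass.

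The cost is one sentence in three places, and no subjects beyond the expansion to 6 that the protocol already provides for.

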5.4 Concomitant Medications (and Procedures)

Concomitant treatment is permitted if the medication is not expected to interfere with the evaluation of safety or efficacy of the study drug. Other antineoplastic therapy for the treatment of the cancer for which subject is enrolled onto this study is not permitted (with the exception of certain standard of care hormonal therapies in consultation with the Medical Monitor). During the study, if the use of any concomitant treatment becomes necessary (e.g., for treatment or prophylaxis of an AE), the treatment must be recorded on the electronic case report form (eCRF), including the reason for treatment, generic name of the drug, dosage, route, and date of administration.

PLX2853 was stable in human liver S9 fractions with 1 metabolite (M1) detected. CYP2C8 and CYP3A4 are the major contributors for the formation of the PLX2853 oxidative metabolite M1. Their relative contributions to the formation of M1 were similar. However, because the rate of metabolism is very low, CYP2C8 and CYP3A4 inhibitors are not expected to have a significant effect on the clearance of PLX2853. Until information regarding exposure-toxicity and exposure-response relationships are available with PLX2853, concomitant CYP3A4 and CYP2C8 inhibitors and/or inducers should be avoided and may be administered after study entry with Medical Monitor approval, in the event they alter the systemic exposure to PLX2853 (see Appendix 2 for an example list of strong CYP3A4/2C8 inhibitors and inducers).

No routine prophylactic anti-emetic treatment is required at the start of study treatment; however, subjects should receive appropriate anti-emetic treatment at the first onset of nausea or vomiting and as required thereafter, in accordance with local treatment practice guidelines.

As per international guidance on antiemetic use in cancer subjects, generally, a single-agent antiemetic should be considered (NCCN 2020; Roila 2016).

Locally acting antacids may be used for initial presentation of gastroesophageal reflux disease (GERD). If locally acting antacids do not properly control GERD, proton pump inhibitors and other gastric pH modifiers may be used. All antacids, proton pump inhibitors, and other gastric pH modifiers should be administered 2 hours after PLX2853 administration.

The use of biotin (i.e., Vitamin B7) or supplements containing biotin higher than the daily adequate intake of 30 μg is prohibited during the study (NIH-ODS 2020). A total daily dose of 30 μg or less is allowed. Use of herbal, alternative, and food supplements (i.e., PC-Spes, Saw Palmetto, St. John's Wort, etc.) and probiotics must be discontinued before treatment start. Daily multi-vitamin (provided it does not contain biotin >30 μg /day), calcium, and Vitamin D are permitted.

Concomitant medications known to prolong the QT interval (see Appendix 4) are prohibited while receiving study drug (drugs with a low risk of QTc prolongation that are needed for infection control or nausea may be permitted with approval from the Medical Monitor).

All ongoing medications and therapies (including herbal products, nutritional supplements, and nontraditional medications) at Screening will be considered prior medications. All medications and procedures must be recorded on the appropriate eCRFs at the start of Screening until 30-day FU Visit procedures are performed or until the initiation of a non-protocol therapy for the underlying malignancy, whichever occurs first.

Palliative radiotherapy may be used for the treatment of pain at the site of bone metastases that were present at baseline following the completion of Cycle 1, provided the Investigator does not feel that these are indicative of clinical disease progression during the study period. Study treatment should be discontinued for a minimum of 3 days before a subject undergoes therapeutic palliative radiation treatment and 7 days after completing radiation treatment. Study treatment should be restarted within 21 days as long as any bone marrow toxicity has recovered.

5.5 Precautions and Restrictions

There are no non-medication-related restrictions or precautions.

5.6 Management of Clinical Events

All necessary support care shall be available to subjects. For dose modification guidelines, see Section 6.2.

5.7 Blinding and Unblinding

Blinding methods will not be employed; PLX2853 and carboplatin (if applicable) will be administered in open-label fashion.

5.8 Preparation, Reconstitution, and Dispensation

PLX2853 is an anti-cancer drug and, as with other potential toxic compounds, caution should be exercised when handling PLX2853 (see Section 5.10). Specific instructions on preparation, reconstitution, and dispensation will be provided in the Study Pharmacy Manual.

Carboplatin will be prepared and administered per the label.

5.9 Packaging and Labeling

PLX2853 tablets are manufactured, packaged, and labeled according to Good Manufacturing Practice and Good Clinical Practice (GCP) at the following address:

BioDuro LLC (formerly Formex LLC) [name]

Carboplatin is packaged per the label.

5.10 Storage, Handling, and Accountability

PLX2853 tablets should be stored at room temperature 20°C to 25°C (68°F–77°F); excursions are permitted between 15°C and 30°C (59°F and 86°F). Subjects will be requested to store PLX2853 at the recommended storage conditions noted on the label. Carboplatin will be stored at the recommended storage conditions per the label.

The study drugs provided in accordance with this protocol will be kept in a secure place and will only be supplied to subjects participating in this study. The Principal Investigator is accountable for all study drug supplied by the Sponsor in accordance with this protocol. In addition, the Principal Investigator must keep accurate and up-to-date dispensation records. Any study drug accidently or deliberately destroyed must be recorded in a timely fashion, including an explanation for the destruction in writing. Any discrepancies between the amounts of study drug dispensed and returned must also be explained in writing. All such records of drug accountability must be entered on the corresponding subject eCRFs.

All unused and partially used study drug must be sealed and returned to the Sponsor or designee or destroyed on site in accordance with the established procedures for drug destruction. Details of destruction, including, but not limited to, the number of boxes destroyed, batch number, and the date and method of destruction must be recorded on the study drug destruction logs.

5.11 Other Protocol-specified Materials

Central laboratory kits will be provided for sample collection, shipment, and storage for PK and PDx analyses.

6.0 DOSE-LIMITING TOXICITIES AND DOSE MODIFICATIONS

6.1 Definitions of Dose-limiting Toxicity

DLTs are defined as clinically significant AEs or laboratory abnormalities occurring during the first cycle of study drug administration that are *at least possibly related* to either PLX2853 or carboplatin and clearly unrelated to disease progression, concurrent illness, or concomitant medication, and that meet one of the following CTCAE v5.0 criteria below. DLTs will be evaluated for the monotherapy safety lead-in subjects as well as each Phase 1b (PLX2853 + carboplatin) escalation cohort. Toxicities occurring in treatment Cycle 2 or later will be reviewed and their impact on subsequent dosing levels and frequency assessed.

In Phase 1b (PLX2853 + carboplatin), there will be a 24-hour delay between the first and subsequent subjects enrolled in each dose escalation cohort to maximize the safety of enrolled subjects.

Subjects participating in the optional Food Effect sub-study as well as the monotherapy safety lead-in will be DLT evaluable from the date of first dose and the DLT window for these patients will be 28 days from C1D1.

Subjects who are withdrawn from the study prior to completing the DLT assessment window for any reason other than a DLT will be replaced. Subject numbers must not be re-used.

DLTs are defined as follows:

• Hematologic Toxicities

- Grade 4 neutropenia lasting >7 days
- Grade ≥3 febrile neutropenia
- Grade 4 thrombocytopenia
- Grade ≥3 thrombocytopenia lasting >7 days or associated with clinically significant bleeding
- Grade 4 anemia

Non-hematologic Toxicities

- Any dose reduction required during Cycle 1 due to an AE
- Any treatment delay of >7 consecutive days during Cycle 1 due to study drug-related Grade ≥2 AEs that fail to resolve to baseline or Grade ≤1
- Any case of Hy's law defined as AST or ALT >3 × ULN with concurrent total bilirubin >2 × ULN, absence of cholestasis (elevated alkaline phosphatase (ALP) >2 × ULN), and no alternative etiology which can explain the combination of increased AST or ALT and total bilirubin, such as viral hepatitis A through E, other preexisting or acute liver disease, or another drug capable of causing the observed injury

- Any Grade ≥3 increase in AST/ALT (only for subjects without hepatic metastasis and with baseline values within normal limits)
- AST/ALT >5 × ULN for ≥14 days or any AST/ALT >8 × ULN (only for subjects with hepatic metastasis or with abnormal baseline values)
- Grade 3 nausea, vomiting, or diarrhea that does not resolve to Grade ≤ 2 in ≤ 72 hours
- Any Grade 4 vomiting or diarrhea (life-threatening; urgent medical intervention indicated) irrespective of duration
- Any non-clinically significant Grade 3 or higher electrolyte imbalance that does not correct to Grade ≤1 in ≤5 days
- Any Grade 3 or Grade 4 clinically significant electrolyte imbalance (life-threatening; urgent medical intervention indicated) irrespective of duration
- Unless specifically noted in other DLT criteria any Grade ≥3 (AE or laboratory abnormality) toxicity that does not resolve to Grade ≤2 within 7 days despite maximal medical intervention, except for the following:
 - Grade 3 neuropathy in subjects with pre-existing Grade 2 neuropathy
- Any other Grade ≥3 toxicity (except those noted above) for which either the Principal Investigator or Sponsor deems further dose escalation inappropriate
- Carboplatin Cycle 2 Day 1 dose reduction (AUC not total dose) or carboplatin Cycle 2 Day 1 dose interruption for >7 days
 - An allergic reaction to carboplatin or any AEs associated with the allergic reaction during Cycle 1 will not be considered a DLT. The subject will be noted as inevaluable and will be replaced.
- Any death not clearly due to underlying disease or an extraneous cause

A subject who experiences a DLT may remain in the study and continue receiving study drug(s) at a lower dose if the Investigator deems the potential benefit outweighs the risk and that the subject is not eligible for, and/or interested in, an alternative therapy after consultation and agreement with the Medical Monitor.

AEs occurring in treatment Cycle 2 or later will be collected, analyzed, and discussed with the Study Committee to help inform the selection of doses for subsequent study cohorts, including the option of dose reduction. If cumulative toxicities are observed requiring dose reductions in 1 of 3 or more subjects, dose escalation may be halted and more subjects may be treated at that or a lower dose level.

